#### 3) Muscular soreness or fatigue

Borg Rating of Perceived Exertion Scale (Borg) will be administrated periodically throughout the intervention sessions. Subject will be provided with rest period as needed, in particular if BORG rating  $\geq 17$ .

#### 4) Loss of balance or fall from testing

One research team member will remain next to the subject as long as the subject is donned in the exoskeleton robot to prevent loss of balance or fall whether sitting or standing. If a fall or significant loss of balance occurs, one staff physician will be notified immediately. All adverse events will be reported per CPHS protocol.

#### 5) Possible skin irritation

Local irritation, bruising, swelling, or temporary discomfort following wearing of the exoskeleton may occur. Prior to donning the exoskeleton subject's skin will be inspected by a licensed Physical Therapist for baseline, and compared after doffing. Any differences will be recorded and followed up with the study physician accordingly. All adverse events will be reported per CPHS protocol.

#### 6) Bone Fracture

Subjects will be assessed using the SCI Bone Health Screen, their scores will be reviewed with the subject and an informed consent will be signed. All subjects will be cleared by study physician prior to enrollment in the study. The risk of fracture to the subject is no greater with the use of exoskeleton than conventional weight bearing and walking therapy.

#### Statistics

Descriptive analyses will be used for Aim 1. For Aim 2, outcome measures will be analyzed using separate paired t-test (exoskeleton vs. no-exoskeleton walking). We also plan to plot the trend at pre-and post- training for all outcome measures for each subject (without exoskeleton). Significant level will be set at .05.

This is a pilot study therefore no data is available to calculate sample size. The reason to enroll 15 subjects is based on the limited funds awarded to this project. We anticipate that the data from this study will allow for performance of power analysis to determine effect size and sample size for future studies.

#### Ethics

The study will be performed under the prevue and in accordance with the rules set by the Committee for the Protection of Human Subjects (UT IRB). Potential subjects will be identified by physiatrists working in the outpatient clinic and/or on the inpatient wards at The Institute for Rehabilitation and Research (TIRR) Memorial Hermann. Once identified, the potential subjects will be approached and asked if they wish to discuss a study utilizing exoskeletons (Robotic suits worn on the outside of the body) to help people with incomplete spinal cord injury achieve a better gait pattern (better walking). It will also be explained that choosing not to inquire further about the study will in no way jeopardize the relationship with anyone at TIRR or in the Memorial Hermann system. Once the potential subject agrees he/she will be introduced to either the Principal Investigator or the Study Coordinator. Once the potential subject agrees to discuss the study, the individual and anyone that the potential subject wishes to accompany him/her will go into a private room to discuss the contents of the consent form with either the Principal Investigator or the Study Coordinator. After the consent is reviewed in its entirety, and after allowing ample time for questions, either the Principal Investigator or the Study Coordinator will give the potential subject time to discuss the study with whomever the potential subject cares to discuss the study with. If the subject agrees to enroll in the study, the Study Coordinator or Principal Investigator will review the informed consent form with the subject in its entirety.

#### Data handling and record keeping

The subject's name and demographic information will be collected prior to testing. Each subject will be assigned an identification number which will be used from this point forward. All measurements will be stored according to the identification number. The Study Coordinator's locked office contains a locked file cabinet in which research materials are kept. All computers are password protected and only authorized persons have the access to the electronic files saved in computers. Paper data will be stored in the Study Coordinator's office in a locked file cabinet. Access to the file cabinet will be given to the Primary Investigator and authorized team members. All electronic data stored on the hard drive of the desktop machine will be password protected and available only to the authorized research team members. Identifiable data will be stored for 5 years after

the study is completed. Stored files will be deleted from the portable hard drive after 5 years as well. Identifiable data will be shredded at the end of 5 years after the completion of the study.

## Quality control and assurance

To ensure research integrity, standard written procedures for all tests will be established by the Principle Investigator and the Study Coordinator who will then assess each team member's competence for research conduction on a regular basis. Therefore, the testing protocol will be consistent throughout the entire data collection for this study. All outcome measures (pre and post-test) will be performed by a single masked investigator to ensure consistency with performance of the outcome measures and to maintain an un-biased perspective.

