### Study Design and Procedures

This study is designed to investigate whether using exoskeleton could promote recovery of walking in persons with MS. A total of 15 individuals with MS will be recruited for the study. Screening, assessment and treatment sessions will be held at TIRR, Memorial Hermann. Approximately 18 visits over a 1-month period will be required.

Detailed schedule of assessments is shown in Table.

Assessment	Pre Screening/ Screening	Baseline	Exoskeleton Training 5 session/week, 3 weeks, total 15 sessions	Post-treatment (Within a week)
	Visit 1	Visit 2	Visit 3-17	Visit 18
ICF	X			
I/E Criteria	X			
Demographics	X			
Medical History	X			
Mini Mental State Exam		X		X
Muscle strength		X		X
Range of motion		X		X
Barthel Index		X		X
Modified Ashworth Scale		X		X
Quality of life		X		X
Berg Balance Scale		X		X
Timed Up & Go Test		X		X
6-min walk test		X		X
Physical Demand Measure		X		X
Cognitive Demand Measure		X		X
Timed 25 Feet Walk Test		X		X
Physical Demand Measure		X		X
Cognitive Demand Measure		X		X
Exoskeleton training			X	

Borg Rating of Perceived Exertion Scale		X	
Pain scale		X	
Exoskeleton User Feedback			X

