7. Berg Balance Scale: A 14-item objective measure designed to assess static balance and fall risk in adult populations, with maximum summed score of 56 (higher scores represent better functional outcome). This task will be formed without using exoskeleton at pre-assessment and post-assessment.
8. Timed Up and Go Test: this task involves subject to stand from the standard chair, walk straight for 3 meters, turn around, walk back to the chair and sit down with shoes and assistive devices if any. A standard chair with arm rests will be place at the start of the testing course. A mark will be placed on the floor at the 3 meter distance. Subject will be asked to perform the task as fast as possible without losing their balance. One research member will stand next to the subject to monitor the subject performance to prevent falls. The time to complete the task will be measured and recorded. Subjects will also have recording of electromyography in the lower limbs i.e., sensors will be placed on the skin of the legs and thighs (4 on each leg) to non-invasively record muscle activity during walking. Additional sensors i.e., goniometers will be placed on the skin to non-invasively record joint angles of the hip, knee and ankle on each leg. These will be attached to the skin using hypoallergenic tape. This task will be formed without using exoskeleton at pre-assessment and with and without exoskeleton at post-assessment.

9. 6-minute walk test: Subjects will be asked to walk back and forth in a hallway with or without assistive device (consistent among assessment visits) for 6 minutes. The objective is to cover as much space as possible in 6 minutes. Subjects can slow down or stop to rest if they feel like, but should start walking when they feel they are able. Electromyography sensors will also be placed on the skin of the leg and trunk muscles to measure muscle activity. A research team member will walk behind the subject to prevent loss of balance during the test. This task will be formed without using exoskeleton at pre-assessment and with and without exoskeleton at post-assessment. In this tasks, we will measure physical demands and cognitive demand in separate trials or sessions:

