B. Cognitive demands measure: Cognitive demands during walking with and without exoskeleton will be determined by reaction time using a dual-task paradigm [12]. Dual-task paradigm is commonly used to quantify the cognitive (i.e. attentional) resources allocated during a motor task such as walking and usually entails reciting the alphabet or counting backwards [13]. However, this specific measurement is limited by structural issues involving respiration, vocal responses or motor action of the upper limb (push a button) for which there are shared execution pathways with locomotion [14, 15] could interfere with the primary motor task, despite not being caused by competing demands for limited attentional resources. Thus, we chose a simple reaction task (RT), in which the response will be biting on a pressure sensor to make the response pathways as independent as possible from the motor pathways of locomotion [12]. Subjects will with and without EKSO (use same assistive device) at their preferred speed. The secondary RT task consists of biting a pressure transducer placed in the mouth in response to an unpredictable sensory (will not cause pain) electrical stimulation applied by an electrode on the back of the neck [12] without changing walking speed and pattern. The stimulation intensity will be adjusted for each individual before data collection. Shorter RT indicates that reduced amount of attentional resources are required.

11. Exoskeleton satisfaction questionnaire: After completion of exoskeleton training sessions subjects will complete a survey of 9 questions regarding their experience with the exoskeleton and any feedback they would like to provide.

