### Exoskeleton Training

Subjects will participate in individualized training sessions using Ekso®. Each training session will last up to 60 minutes, 5 days per week for 3 weeks, for a total of 15 sessions.

During the training, subjects will wear a lower extremity exoskeleton robotic walking device. Subjects will participate in individualized treatment sessions which may include: sit to stand, static and dynamic standing balance, weight shifting, walking, turning, and stand to sit. Each training session will last up to 90 minutes (60 minutes of training with 30 minutes for setup, don/doff of device) and training will be held 5 days per week for 3 weeks with a total of 15 sessions.

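### The single assessor cannot be masked to treatment, device condition or visit in this one-group study, so the masking claim should be replaced by a statement of open assessment

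*Combined protocol and SAP*

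**What the plan says.** The masking statement is in the protocol's Quality control and assurance section: "All outcome measures (pre and post-test) will be performed by a single masked investigator". The same sentence gives two purposes: "to ensure consistency with performance of the outcome measures and to maintain an un-biased perspective". Nothing there or elsewhere says what the investigator is masked to, or how.

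The design is described in other sections:

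- **Study Design and Procedures:** "A total of 15 individuals with MS will be recruited for the study". No comparison group or randomisation is described. Baseline testing is Visit 2 and post-treatment testing is Visit 18.
- **Exoskeleton Training:** "Subjects will participate in individualized training sessions using Ekso", for 15 sessions.
- **Outcome Measures, Timed Up and Go, 6-minute walk and Timed 25 Feet Walk:** "This task will be formed without using exoskeleton at pre-assessment and with and without exoskeleton at post-assessment".
- **Outcome Measures, Berg Balance Scale:** "This task will be formed without using exoskeleton at pre-assessment and post-assessment".
- **Outcome Measures, satisfaction questionnaire:** "After completion of exoskeleton training sessions subjects will complete a survey of 9 questions".
- **Statistics:** for Aim 2, "outcome measures will be analyzed using separate paired t-test (exoskeleton vs. no-exoskeleton walking"). Pre- and post-training values without the device are to be plotted for each subject.

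**The concern.** Masking an assessor protects against expectation bias only if there is something the assessor does not know. In this plan the three things that matter (what treatment the subject had, whether the device is being worn, and whether this is the visit before or after training) are all apparent to the person doing the test.

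Two things are at stake. First, several outcomes depend on the rater's judgement or the subject's effort: Berg, Modified Ashworth, range of motion, dynamometer strength with verbal encouragement, and the timed and distance walks. The hypotheses in the Objectives section favour the device and the training, so an assessor's expectations could push these measures in that direction. Second, the Publication Plan foresees peer-reviewed papers. A paper that reported masked assessment would credit the study with a safeguard it did not have.

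**Working it through.** The plan gives no figure for masking or bias, so there is nothing of its own to reproduce. The check is mainly one of design logic, followed by one illustrative calculation.

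**Step 1. What could the assessor be masked to?**

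| Possible target | What the plan describes | Can it be hidden? |
|---|---|---|
| Treatment received | All 15 subjects train with the exoskeleton; no other group | No: there is no allocation to conceal |
| Device condition | Timed Up and Go, 6-minute walk and 25-foot walk done with and without the device after training | No: a powered leg exoskeleton is in full view of the tester |
| Visit (pre or post) | Same tester at Visits 2 and 18; with-device trials and the device survey occur only after training | No: the tester did the baseline, and the post-training visit identifies itself |
| Earlier scores or training records | Not described | Possible, but it would hide neither visit nor condition |

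The consistency purpose of the sentence is met by using one tester. The freedom-from-bias purpose is not.

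**Step 2. Which outcomes are exposed, and in which analysis?**

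- *Compared with and without the device by paired t-test (Aim 2):* the walking tasks. The two measures that Aim 2 names, oxygen cost and bite reaction time, are recorded by instruments and leave less room for rater judgement. The walk times and distances depend more on effort and on how the trial is conducted.
- *Compared pre to post by individual plots, with no test stated:* among others Berg, which is done without the device at both visits, and Modified Ashworth, range of motion and strength, which are done on an examination table with no device condition described.
- *Self-reported:* MSQOL-54, where assessor masking would do little in any case.

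**Step 3. What would a bias of a given size do to the planned t-test?**

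Inputs: n = 15 and level .05, from the protocol. Assumptions: two-sided testing (the Statistics section does not say), all 15 pairs complete, no true effect, and a bias of b standard deviations of the paired difference. The values of b are illustrative and come from no source.

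Under these assumptions the t statistic has a noncentral t distribution with 14 degrees of freedom and noncentrality b × √15. The critical value is 2.145. The rejection probability is P(|T| > 2.145).

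| b (SD of paired difference) | b × √15 | Rejection probability |
|---|---|---|
| 0 | 0 | 0.050 |
| 0.2 | 0.775 | 0.112 |
| 0.3 | 1.162 | 0.192 |
| 0.5 | 1.936 | 0.438 |

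These rates belong only to the with-device versus without-device walking outcomes. They say what a bias of that size would do, not that such a bias will occur.

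**The case against.** The strongest case on the other side has five parts.

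1. *The harm is limited.* This is a 15-subject, funding-limited pilot, Aim 1 is descriptive, and Aim 2 is already framed around oxygen cost and reaction time. Any reader of a report would see one group and a visible device. This stands as a reason for proportion. It does not make the sentence correct, because it asserts a property that the design cannot have.

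2. *Masked may have been meant narrowly,* for example to baseline scores, training records or the level of trainer assistance. That is possible and would keep some protection. The plan does not say so, and the stated purpose is general. This stands as a reason to allow a definition rather than insist on deleting the word.

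3. *The false-positive rates could be read too widely.* A reader might infer that Berg, Modified Ashworth, range of motion and strength carry an 11% to 44% error rate. The documents do not support this: the paired t-test is planned only for walking with and without the device, and the pre/post measures are plotted. For those the risk is a distorted trend plot and a distorted basis for later power calculations, not an inflated test.

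4. *A reader might also infer that the walks are timed by hand and so especially open to bias.* The plan says only that time is measured and recorded, and the 25-foot walk also has motion capture. No claim about the timing method is made here.

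5. *Coded files may not hide the condition.* EMG and motion-capture signals may themselves show that the device was worn, and with-device files exist only after training, so recognising the condition also reveals the visit. This stands, and the file-coding part of the fix is limited accordingly.

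**Conclusion.** The point holds. As written, the masking statement is wrong for treatment, device condition and visit, and this follows from the plan's own description of its groups, test conditions and assessor. It is more than a missing detail, since the sentence claims freedom from bias as a result. It would go too far to say that the arrangement has no value, because one tester does give consistency between visits.

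The size of any bias cannot be derived from the documents. The illustrative range of 11% to 44%, against a nominal 5%, rests on assumed shifts of 0.2 to 0.5 SD, two-sided testing and 15 complete pairs, and is confined to the with/without-device walking comparisons. The study can go ahead, but the statement should be corrected before results are reported.

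**What to change.** 1. In Quality control and assurance, replace the masking claim with a statement that one investigator, not masked to visit or device condition, performs all pre- and post-test measures for consistency. If narrower masking is actually applied, such as to baseline scores or training records, name it and say how it is maintained.
2. State open assessment as a limitation for Berg, Modified Ashworth, range of motion, strength, and the timed and distance walks, both in the plan and in any report.
3. Have existing staff process the oxygen and bite reaction-time files under codes that hide visit and condition until artefact, outlier and time-window decisions are locked. The plan already de-identifies its data by subject code, so this extends current practice.
4. For EMG and motion capture, acknowledge that the signal may reveal the device and that coding may not mask the analyst.
5. If false-positive inflation is illustrated anywhere, confine it to walking outcomes compared with and without the device, and label the shifts as assumptions.

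The cost is a change of wording and a small file-coding step, with no extra assessor or visits. The downside is a less favourable statement about bias control.

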## Publication Plan

The results of this study will be used for presentation at national conferences and publications in peer-reviewed journals. The publications will be provided without cost to the study participants.

## ATTACHMENTS

1. Physician clearness letter
2. Phone Screening Form
3. Case Report Forms (pre and post-test outcome measures)
4. Barthel Index
5. MMSE
6. Quality of life measure
7. Berg Balance Scale
8. BORG Rate of Perceived Exertion Scale

